This section is not applicable to my study

1. Where will the devices be stored?	Explain. Devices are stored in the Operation Room (OR) and are in stock in the OR holding room at New Hanover Regional Medical Center.
2. Who will receive and manage inventory for the devices throughout the study?	Name: OR Staff Title: Nurses and Doctors
3. Who will have access to the devices?	Name: OR Staff Title: Nurses and Doctors
4. How will the devices be accounted for?	Explain. Devices that are available on stock at the hospital will be used and the Lot number will be recorded.

5. What protections are in place to prevent loss or improper use?	Explain. These are devices are currently FDA approved and used on a daily basis at NHRMC so there are already precautions in place to protect them.
---	---

Part II: Study Subjects and Procedures

Complete the sections that apply to your study.

A. Subject Enrollment and Demographics:

This is a listing of the **target** study population. Check all that may apply.

You don't have to meet the anticipated subject enrollment number, but you can't exceed it without an amendment to increase the number anticipated at this site.

 Healthy Volunteers	 Chronically Ill	 Placebo (non active medicine)
 Employees	 Mentally Ill	 No Treatment Condition (control group is involved that receives no study-related treatment)
 Students	 Terminally Ill	 Storage of Specimens for Future Use
 Hospitalized Patients	 Use of Banked Specimens	 Multi-center Study: Subject Enrollment
 Male	 Use of Fetus/Fetal Tissue	# anticipated this site
 Female	 * Indigent/Uninsured	 Single Site Study: Subject Enrollment
 Adults	 * Non-English Speaking	# anticipated this site 511
 Children (under 18) (complete section V)	 * Limited or No Literacy	
 * Pregnant (see below)		

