
2. Description of study design, methods, and procedures, describe the study in sequential order as it is to be conducted at this institution. The following should be included:
 
 ➤ type of experimental design ➤ study procedures: a sequential description of what will be asked of/done to subjects (to include identification and recruitment of subjects, consent process, treatment or intervention if applicable, length of participation, additional visits, follow-up, etc.) ➤ description and assignments of subjects to various arms of the study (if applicable) 	
This will be a prospective open-label randomized study conducted by [name] from the study's approval date to until December 31, 2015. Approximately five-hundred (500) subjects will be enrolled in this study.
 
Patients presented to NHRMC, the Outpatient Surgery Clinic, SEAHEC Physicians' Office, Inpatient Surgical Units at NHRMC and/or the Emergency Department for abdominal wall hernia repair during their pre-operative visit and who meet the inclusion and exclusion criteria will be counseled by [name] on surgical options for repair to determine if they would

- doses, frequency, and route of administration of medication and other treatment
- data that will be collected
- primary outcome measurements
- follow-up procedures
- If the study involves clinical activities, distinguish routine care procedures from those that are study specific

rather undergo an open or laparoscopic repair. If the patient is a candidate and agrees with undergoing the laparoscopic repair, they will be asked if they would like to participate in a randomized trial comparing two different meshes. If the patient agrees, he/she will be presented with information regarding this study. The study will then be explained to the patient by [name].

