helps patients to say how good or bad their health state is. This scale uses a line with two different extremes. The extremes can vary in forms. Some VAS can ask the patient to range their pain level or current health status on a rating of either 0-10 (with 0 being no pain and 10 being the worst possible pain) or by choosing a picture of a happy or sad face.

Patients with bilateral inguinal hernias (an abnormal opening or defect that occurs on both sides of the groin), either found preoperatively or intra-operatively, will be treated as one hernia and will have the same mesh placed on both sides. Cases will be performed by one attending using his standard technique for laparoscopic inguinal hernia repair.

Data to be collected will include the patients' demographic information (age, sex, race), comorbidities (if present), smoking history, drinking history, medications, allergies and previous surgeries.

Operative data will include the following: type of anesthesia (all patients will undergo general), technique of laparoscopic access, type and side of hernia (direct or indirect), size of mesh used, type and number of tacks used to secure mesh, operative time, blood loss, urine output, and type and technique of closure.

Postoperative data will include: length of hospital stay, perioperative complications, recurrence rate, patient pain score and patient's postoperative quality of life. Further follow up data will include an assessment of the patient's recurrence rate, pain scale and quality of life during the patient's 1-2 weeks, 6 months, and 1 year follow-up. The patient will also be asked to rate their pain and/or comfort level by using the CCS and/or the VAS. During their 1-2 weeks visit, the patient will be informed of the 6 and 1 year follow-ups. For the six (6) month and one (1) year follow-up the patient will be contacted by telephone and/or be asked to return to the SEAHEC Physician's Office. The patient will not be charged for any of these services. Subjects will be tracked and identified with the use of the research record that will be set up in EPIC. Patients will be associated with the study and their surgery admission will be associated with the study for billing and coding compliance. In case the above system does not work, as a secondary system, patients will be tracked using an excel spreadsheet.

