Resident will be approached by [name] prior to the initiation of the study. [name] will give the residents the information sheet and will explain the study to the

	
residents. Additional time to review the information sheet will be provided if needed. [name] will address and answer all concerns and questions of the residents pertaining to the study. If the residents agree to participate in the study, the study coordinator will obtain verbal consent from the consenting residents. There will be no repercussions to any residents that objects to being in the study.
 
Resident level (PGY level), participation in the case (percentage of resident involvement to be determined by attending physician), time to perform the three critical portions of the case (laparoscopic access and takedown of peritoneum, placement of mesh, closure of peritoneum, and closure) will all be documented. This is routinely done by the surgical residents.
 
Following the case, the resident will be given a performance scale (NASA-TLX) to grade his/her performance in conducting the surgery. This is not routinely done but is done for some surgical cases. The NASA-TLX is a publicly available, multi-dimensional scale designed to obtain workload estimates from one or more operators while they are performing a task or immediately afterwards. It contains 6 scales that will ask the residents to rate their mental demand, physical demand, temporal demand, performance, effort and frustration on a scale of very low to very high. This will take the resident no more than three (3) minutes to complete. Once the resident has completed the scale, they will return the scale to [name]. [name] will then give the scales to the study coordinator who will keep all the scales in a locked and secure place at SEAHEC. The scale will be linked to the study patient by entering the study patient's study ID number on the scale. The residents do not routinely complete the NASA-TLX for all surgeries but for some they do. The requirement for the completion of the NASA-TLX by the surgical residents will be new and specific for this study.
 
Descriptive statistics will be performed and outcomes and resident performance will be compared based on resident level and type of mesh used. A p-value of <0.05 will be considered significant.

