
4. Inclusion/exclusion criteria: List required elements of potential subjects and those that preclude enrollment. (Exclusion criteria are not opposite of inclusion criteria, but rather elements within the already identified subject population that would be a cause for exclusion from the study.)
	
The inclusion criteria for patients in this study will include all of [name] patients undergoing laparoscopic repair for the treatment of either single or bilateral inguinal hernias from the study's approval date to December 31, 2015.
 
The inclusion criteria for residents in this study will include all surgery residents.
 
The exclusion criteria for patients in this study will include patients requiring emergency surgery, pregnant patients and patients under 18 years of age.
 
There is no exclusion criteria for residents in this study.

Part V: Financial Conflict of Interest

[figure not shown]
This section is to be completed for all financially sponsored studies.

Are you being paid to conduct this study? Yes No

If yes, complete questions below, if no skip to next section.

If financially sponsored indicate source:

Indicate by marking YES or NO if any of the financial interests or arrangements described below apply to you, your spouse, or dependent children.
		
Yes 	No 	Compensation for services (e.g. consulting fees or honoraria), or in-kind payments, other than from the Investigator's primary employer, in the prior calendar year or project over the next twelve months.
		Royalty income or the right to receive future royalties under the patent license or copyright,

		where the research is directly related to the licensed technology or work.
		Equity interests (e.g. stocks, stock options or other ownership interests, including equity holdings where the value cannot readily be determined by reference to public prices).
		Intellectual property rights (e.g. patents, copyrights, and royalties from such rights).
		Gifts or funds available to the researcher from this sponsor beyond the current research project.
		Funding expected to significantly exceed the projected costs of conducting the current research project.

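### Surgery and study conduct end on the same date, and the plan names no method for patients with less than one year of follow-up

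*Combined protocol and SAP*

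**What the plan says.** All references are to the combined protocol and SAP, Part IV.

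- **Study period (item 2).** The study is to be conducted "from the study's approval date to until December 31, 2015". The approval date is not given.
- **Eligibility (item 4).** Patients qualify if they undergo laparoscopic repair of "single or bilateral inguinal hernias from the study's approval date to December 31, 2015". The closing date for surgery is therefore the closing date for study conduct.
- **Size.** Item 2 states: "Approximately five-hundred (500) subjects will be enrolled in this study". The enrolment table in Part II, section A gives 511.
- **Follow-up (item 2).** The plan assesses "recurrence rate, pain scale and quality of life during the" follow-up visits at 1-2 weeks, 6 months and 1 year. The two later contacts may be by telephone or at the office, at no charge. Pain and comfort may be rated on the Carolinas Comfort Scale (CCS), the visual analogue scale (VAS), or both.
- **Analysis (item 2, last paragraph).** "Descriptive statistics will be performed and outcomes and resident performance will be compared" by resident level and mesh type, with significance at p<0.05. No test or model is named.

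Nothing sets a last surgery date one year before the end, a follow-up phase after it, a data cut-off, a denominator for the recurrence rate, or a rule for incomplete follow-up.

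**The concern.** Recurrence, pain or comfort, and quality of life are among the effectiveness measures listed in item 1, so this touches the main purpose of the trial. Read literally, the two dates make follow-up unequal by design: a patient operated on in December 2015 could contribute days or weeks, while an early patient contributes the full year.

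Unequal follow-up makes either simple summary of recurrence unsatisfactory. If all enrolled patients form the denominator, those seen only briefly count as recurrence-free at one year. If only those who reached one year are counted, the shorter follow-up of later patients is thrown away. The same loss affects a 1-year comparison of scores. Because the trial is open-label and no denominator is fixed in advance, the choice could also be made after the results are known.

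**Working it through.** **No figure to reproduce.** The documents give no recurrence rate, effect size, standard deviation, dropout rate or power behind the 500 or 511. What follows is an illustration.

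**Inputs from the documents:** end date December 31, 2015 for both surgery and conduct; visits at 1-2 weeks, 6 months and 1 year; 500 patients; two arms.

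**Assumptions:** data stop on the end date; even accrual over A years up to that date, with A from 1.5 to 5 because the approval date is unknown; constant recurrence hazard; 250 patients per arm; first visit at 2 weeks; for power, a difference of 0.25 SD and two-sided 5% significance.

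**Step 1: share without follow-up.** Share without one year = 1/A; share without 6 months = 0.5/A. For A = 3: 1/3 of 500 = 167 lack one year, and 83 of these also lack 6 months. So about half of those without one year do reach 6 months.

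**Step 2: crude recurrence over all enrolled.** Let p be the true 1-year risk and t the available follow-up, uniform on 0 to A. Crude rate = mean of 1 - (1-p)^min(t,1). For p = 5%, A = 3:

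- Patients with a full year contribute (2/3) × 5% = 3.33%.
- The average risk over a partial year is 1 - p/(-ln(1-p)) = 1 - 0.05/0.0513 = 2.52%, contributing (1/3) × 2.52% = 0.84%.
- Total 4.17%, which is 83.5% of the true 5%.

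If recurrence is found only at scheduled visits, t is rounded down to the last visit reached, and the crude rate is 3.79%, or 75.7% of the true value.

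**Step 3: completers only.** The standard error is multiplied by 1/sqrt(1 - 1/A). With 250 per arm and full follow-up, power for 0.25 SD is 80%.

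| A (years) | Without 1 year (of 500) | Crude ÷ true, detected at any time | Crude ÷ true, scheduled visits only | Completers per arm | Rise in SE | Power, completers |
|---|---|---|---|---|---|---|
| 1.5 | 333 (67%) | 67.0% | 51.4% | 83 | 73% | 37% |
| 2 | 250 (50%) | 75.2% | 63.6% | 125 | 41% | 51% |
| 3 | 167 (33%) | 83.5% | 75.7% | 167 | 22% | 63% |
| 4 | 125 (25%) | 87.6% | 81.8% | 188 | 15% | 68% |
| 5 | 100 (20%) | 90.1% | 85.4% | 200 | 12% | 71% |

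The ratios are for p = 5%; taking p from 1% to 10% moves them by less than one percentage point. With 511 patients, the number without one year runs from 341 down to 102, so the 500/511 difference does not matter here.

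**Step 4: gain from a repeated-measures model, A = 2.** The shares with 1-year and 6-month data are 0.50 and 0.75. With correlation r between those visits, effective n per arm = 250 / ((1-r²)/0.50 + r²/0.75).

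- r = 0.5: 250/(1.500 + 0.333) = 136, power about 54%.
- r = 0.7: 250/(1.020 + 0.653) = 149, power about 58%.

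Completers only: 125 per arm, 51%.

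**The case against.** The strongest reply is that the harm is conditional. Item 4 is an inclusion window, and item 2 promises 6-month and 1-year contacts without exempting late patients, so contacts may have been meant to continue past the end date. That stands: no data cut-off is stated. But item 2 also ends study conduct on that date, and nothing reconciles the two.

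Several stronger readings are tempting, and the documents do not support them:

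- **That the plan's recurrence figure is wrong as stated.** No recurrence summary is defined. The rate appears in a list of data to collect and can be read as a per-visit assessment. A proportion among patients assessed at one year is not understated by purely administrative cut-off.
- **That understatement and data loss both occur.** For recurrence they follow from alternative denominators.
- **That outcomes are only described.** A comparison by mesh at p<0.05 is planned; what is missing is the method.
- **That telephone follow-up will lose patients.** The plan offers telephone or office contact free of charge, which could equally help retention.
- **That the mesh comparison is biased.** Randomisation should make administrative cut-off similar in both arms. Bias needs loss that differs by mesh.

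It is also fair that a mixed model recovers little of the lost power, and that the recurrence ratios depend on how recurrences are detected, which is why both versions are shown.

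**Conclusion.** The point holds in conditional form. Established from the text: surgery and conduct share an end date, 1-year outcomes are planned, and no method deals with incomplete follow-up. If data stop on that date, every patient operated on in 2015 lacks the 1-year assessment. The proportions and the size of any understatement then rest on even accrual over an unknown period, a constant hazard and an all-enrolled denominator; the power figures rest on the assumed 0.25 SD. Even at the five-year end of the range, one patient in five lacks 1-year data. The consequence is either an absolute recurrence rate that is too low to read as a 1-year risk, or a loss of precision. It is not evidence of a biased comparison between meshes. The change should be made, and most of it is wording.

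**What to change.** 1. Reconcile items 2 and 4 by stating whether follow-up continues after December 31, 2015 until each patient's 1-year contact. This comes first, because analysis alone recovers only a small part of the lost information.
2. Analyse recurrence as time from surgery, censored at the last contact. Report the 1-year Kaplan-Meier estimate by randomised mesh, or a life-table estimate on the visit intervals if recurrence is found only at scheduled contacts, with a log-rank or similar comparison.
3. Analyse CCS and VAS separately, each with a repeated-measures mixed model over the visits at which that instrument was collected. Adjust for the preoperative score where it is meaningful; the CCS item on sensation of mesh has no clear meaning before surgery.
4. Report missing data by mesh and visit, with one sensitivity analysis that shifts the unobserved values.

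**Cost.** Analysis wording, the date of each contact, slightly more analysis work, and a stated missing-at-random assumption. The mixed model's gain over completers is modest: about 51% to 54-58% power in the 24-month example. If follow-up does continue for everyone, steps 2 to 4 remain useful for ordinary loss to follow-up.

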2. Will the subject be financially responsible should insurance deny coverage of study-related costs?	 No  Yes	The six (6) month and one (1) year follow-up visit are not routine, therefore, the patient will not be charged for any of these services (both clinic and professional fees will not be billed to the patients). For the 6 month and 1
3. Will the subject be financially responsible should insurance deny coverage of routine care costs?	 No  Yes	

4. Will the PI or a representative discuss with the subject the difference between study related costs and routine care costs, and that the subject or the subject's insurance provider will be responsible for routine care costs?	 No  Yes	year follow-up the patient will be contacted by telephone or be asked to return to the SEAHEC Physician's Office. [name] will discuss this information with the patients.
---	---	---

G. Statistical Analysis

1. Who will provide statistical analysis?	SEAHEC Research Department
2. Is there a data safety monitoring board?	 No  Yes  N/A, this is not a clinical trial or treatment study

Part IV: Description of Proposed Research Study

NOTE: This portion of the application is not intended for a cut and paste from the protocol, but rather for a summary of why the study is needed and how the study will work at this institution. **Please use lay terms or provide definitions.**

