	
One main part of the procedure to repair a hernia involves the placement of a prosthetic (a device that substitutes for missing parts or pieces) mesh to reinforce the abdominal wall and allow for a tension free repair. The use of the mesh also helps to lower the recurrence rate (the chance that the hernia will come back). The most common type of mesh prosthesis that is placed in laparoscopic inguinal hernias is a polypropylene (the substance the mesh is composed of) mesh which has been shown to be safe and effective.
 
There is some emerging evidence that a "lighter weight" form of this mesh may improve quality of life outcomes following surgery and is the mesh currently being used at New Hanover Regional Medical Center for laparoscopic inguinal hernia repair. However, there are many different "light weight" polypropylene meshes on the market that are FDA approved and available for use. Currently, there are two different forms of the mesh being used interchangeably for the procedure at NHRMC. Both of these meshes have had good clinical outcomes.
 
The purpose of this research study is to evaluate the clinical effectiveness of the two meshes currently being used. The study may provide evidence on whether one mesh is more effective than the other. A secondary goal of the study is to evaluate the ease of use and time it takes residents to place and perform the surgery using these two different meshes. This information may make it possible to determine if one mesh is easier for residents to use during surgery and therefore take them less time to perform the procedure.
 
The effectiveness of the meshes will be measured by the patient's length of hospital stay, perioperative complications, recurrence rate, patient pain score and/or comfort level and the patient's postoperative quality of life.

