[name] will give the patients the informed consent document at New Hanover Regional Medical Center, Outpatient Surgery Clinic, SEAHEC Physicians' Office, Inpatient Surgical Units at NHRMC and/or the Emergency Department. [name] will review the page-by-page informed consent document with the patients. A copy of the informed consent document explaining the objectives and associated risks and benefits of the study will be given to the patient. The patient will be allowed to read and review the elements of the informed consent document. Patients will have a chance to ask [name] any questions they may have about the surgery and the study. If necessary, the patient will be allowed additional time to review the document. After receiving verbal consent, [name] will obtain written consent from the patient. A copy of the signed informed consent document will be given to the patient and another copy will be placed into the patient's medical record. The original document will be placed into a separate secure file cabinet that will be locked at all times.

On the day of surgery, patients agreeing to participate in the study will be randomized to receive either one of two meshes - ultrapro mesh (Ethicon) or bard 3d max (Bard). This randomization will occur with a random pattern being generated using an electronic random number generator. Then, the random assignments will be placed inside opaque, sequential envelopes. The envelopes will be opened, in order, which will guarantee a random assignment of subjects to each study arm.

Prior to the surgery, patients will be given the Carolinas Comfort Scale (CCS) and Visual Analog Scale (VAS). These study specific scales will be used to access the patients' pain and/or comfort level prior to surgery and should take no longer than 5 minutes to complete. The CCS uses a patient questionnaire of 8 questions to establish a quality measure for pain. Patients are asked to rate, on a scale of 0 to 5, sensation of mesh, pain and movement limitations during the following activities: lying down, sitting up, activities of daily living, coughing or deep breathing, walking or standing, walking up or down stairs, and while performing non-work related exercising. The VAS

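### Both pain/comfort scales are given before surgery, but follow-up allows either one and no form of the VAS is fixed; the baseline scores have no stated role in the analysis

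*Combined protocol and SAP*

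**What the plan says.** All of the relevant text is in the combined protocol and SAP, mostly in Part IV, item 2 (design, methods and procedures).

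- **Before surgery.** Both scales are given: "patients will be given the Carolinas Comfort Scale (CCS) and Visual Analog Scale (VAS". Their stated purpose is descriptive: "These study specific scales will be used to access the patients' pain and/or comfort level prior to surgery". The CCS is described as 0-5 ratings of mesh sensation, pain and movement limitation across a list of activities.
- **Form of the VAS.** The description is generic: "Some VAS can ask the patient to range their pain level or current health status on a rating of either 0-10", with a happy or sad face picture as the alternative. The text adds that the extremes of the line can differ. No section picks a form.
- **Follow-up.** At 1-2 weeks, 6 months and 1 year: "Further follow up data will include an assessment of the patient's recurrence rate, pain scale and quality of life". That sentence names no instrument. The next one does: "The patient will also be asked to rate their pain and/or comfort level by using the CCS and/or the VAS".
- **Contact at 6 months and 1 year.** "the patient will be contacted by telephone and/or be asked to return to the SEAHEC Physician's Office". Part II, section F also provides for telephone contact.
- **Role of the outcome.** Part IV, item 1 lists "patient pain score and/or comfort level and the patient's postoperative quality of life" among the effectiveness measures, after length of stay, complications and recurrence. None is called primary.
- **Analysis.** The last paragraph of Part IV, item 2 is the only analysis statement. It provides for descriptive statistics, comparison by resident level and mesh type, and a 0.05 threshold. It does not mention the baseline scores.

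**The concern.** The baseline rule requires both scales, while the follow-up rule accepts either. Read as written, a patient with only a CCS and a patient with only a VAS have both met the protocol, yet they share no follow-up score. The two scales cannot stand in for each other: one is a set of activity ratings from 0 to 5, the other a single rating. The same problem can arise within the VAS if some patients rate pain and others health state, or some give a number and others choose a face.

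Pain/comfort is one of the measures on which the meshes will be judged, and a rating missed at its visit cannot be obtained later. What is at stake is the usable sample, and so the precision, for that measure.

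The second part is smaller. Baseline scores are collected from everyone, but the analysis paragraph does not use them. Adjusting for a baseline score that correlates with the outcome narrows the interval without collecting anything more.

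**Working it through.** **The plan's own figures.** The documents give about 500 subjects (Part IV, item 2; the enrollment box in Part II, section A gives 511) and a 0.05 threshold. They give no power, effect size, SD, dropout or completion rate, so there is no stated calculation to reproduce. What follows is an illustration, not an estimate for this trial.

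**Step 1: the text, side by side.**

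| Time | Scales required | VAS form |
|---|---|---|
| Before surgery | CCS and VAS | not fixed |
| 1-2 weeks, 6 months, 1 year | CCS, or VAS, or both | not fixed |

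No rule assigns a scale to a patient or a visit.

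**Step 2: interval width.** Assumed: 1:1 allocation (250 per arm), two-sided 0.05, no dropout, SD = 1. The half-width of the 95% CI for a difference in means is t × √(2/n), where n is the number per arm who completed that scale in the same form.

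| Completion | n per arm | t × √(2/n) | Half-width (SD) | Wider by |
|---|---|---|---|---|
| 100% | 250 | 1.965 × 0.0894 | 0.176 | 0% |
| 90% | 225 | 1.965 × 0.0943 | 0.185 | 5% |
| 75% | 188 | 1.966 × 0.1031 | 0.203 | 15% |
| 50% | 125 | 1.970 × 0.1265 | 0.249 | 42% |

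The widening does not depend on the effect size.

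**Step 3: power.** This does depend on the effect size (two-sample noncentral t, same assumptions).

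| True difference | 100% | 75% | 50% |
|---|---|---|---|
| 0.20 SD | 61% | 49% | 35% |
| 0.25 SD | 80% | 68% | 50% |
| 0.30 SD | 92% | 83% | 66% |
| 0.40 SD | 99% | 97% | 88% |

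At 0.40 SD the loss from 75% completion is small. Using 511 rather than 500 subjects barely changes the picture: the difference detectable with 80% power is 0.248 SD instead of 0.251 SD.

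**Step 4: baseline adjustment.** With baseline-to-follow-up correlation r, ANCOVA multiplies the residual variance by 1 − r², so power is evaluated at d/√(1 − r²). For d = 0.25 and 250 per arm:

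- r = 0.1: 0.25/√0.99 = 0.251, power 80% (no useful gain)
- r = 0.3: 0.25/√0.91 = 0.262, power 83%
- r = 0.5: 0.25/√0.75 = 0.289, power 90%

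Part IV, item 3 expects very mild pain, so scores may bunch near zero, which weakens the correlation. With an assumed 70-85% zeros and an underlying correlation of 0.4, the observed correlation was about 0.24-0.30 in a simulated check. At r = 0.24, 0.25/√0.9424 = 0.258 and power is 82%. In a separate simulation under the same assumptions with no true difference, the ANCOVA false-positive rate was 4.3-5.0%, so adjustment did not inflate error.

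**Step 5: number of comparisons.** Two scales at three visits make six comparisons. If they were independent and each tested at 0.05, the chance of at least one false positive would be 1 − 0.95⁶ = 26%. Positive correlation between them would lower it. This is why the fix names a lead comparison.

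**The case against.** The strongest case is about genre. The note that opens Part IV asks for a summary in lay terms, not text pasted from a protocol. On that reading the VAS passage defines such scales in general and does not authorise mixed forms, and calling the scales study specific suggests that a set form may exist. The document also uses *and/or* loosely elsewhere, including where both scales are plainly given. Staff may well intend to collect both at every visit.

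Much of this stands. The text permits a single scale; it does not plan for one. The completion rates above have no source in the documents. Even so, no section names a form or requires both scales at follow-up, and if the intention is already to collect both in one form, the correction only puts that in writing.

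It is also fair to say that baseline adjustment is a choice, since the analysis paragraph names no test for any outcome. That is why it ranks second here.

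Four stronger readings are tempting but not supported:

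- **That patients will end up without a common score.** Nothing in the documents says so.
- **That the trial is biased because an open-label team could choose scales differently by arm.** Nothing excludes it, but nothing indicates it.
- **That telephone versus office contact distorts the comparison.** It would do so only if contact mode differed between arms, and the documents give no sign of that. Telephone contact matters here only because a line or a picture is hard to give by telephone.
- **That leaving out baseline makes the comparison invalid.** Randomization protects it either way.

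The opposite reading, that nothing is lost if everyone completes both scales, also goes too far: VAS ratings taken in different forms would still not be comparable.

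**Conclusion.** The concern holds as a gap in the follow-up rule that should be fixed; it does not show that the trial is flawed. Both scales are required at baseline, either one suffices at follow-up, and no VAS form is fixed at any time.

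The size of the loss depends on what happens in practice. It is nil if every patient completes both scales in one form. It is a 15% or 42% wider interval if 75% or 50% complete a given scale in that form, assuming 250 per arm and no dropout. The power cost ranges from appreciable at 0.25 SD to slight at 0.40 SD.

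The unused baseline scores are a lesser matter of precision. At an assumed correlation of 0.3-0.5, adjustment raises power at 0.25 SD from 80% to 83-90%, with less gain if scores bunch near zero. Effect size, completion and correlation are all assumptions.

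**What to change.** **1. Data collection (main change).** In Part IV, item 2, name one VAS form in the pre-surgery text and again in the follow-up text. Use the existing study form if there is one; otherwise, for example, the 0-10 pain rating with the anchors already given there. Replace the either/or follow-up sentence with wording such as:

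> Every patient will complete both the CCS and the named VAS form before surgery and at 1-2 weeks, 6 months and 1 year. The form used can also be given by telephone.

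If the VAS was meant to measure health state for the quality-of-life outcome, say so and keep that item, so that fixing a pain rating does not remove it.

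**2. Analysis.** In the analysis paragraph of Part IV, item 2:

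- Compare each scale between meshes at each visit, adjusted for its baseline score.
- Score the CCS by the instrument's own rule and cite it. The protocol mentions eight questions but lists seven activities, so a rule cannot be built from its text.
- Leave mesh sensation out of the CCS baseline covariate, since it generally cannot be rated before a mesh is placed. The covariate need not be the same score as the outcome.
- Name one scale and one visit as the lead pain/comfort comparison. Report the other five as supportive, with 95% CIs.
- Report the number completing each scale by arm and visit.

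**Cost.** Changes to protocol, form and analysis wording; at most one short extra scale at each planned contact; slightly more analysis work. The protocol puts the pre-surgery scales at no more than 5 minutes in total. It does not say whether that holds by telephone. No new visits or calls are needed.
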